## ABBREVIATIONS

AE	Adverse event
AR	Adverse reaction
BNF	British National Formulary
CI	Chief Investigator
CRF	Case Report Form
CRP	C-Reactive Protein
CTU	Clinical Trial Unit
CTIMP	Clinical Trial of an Investigational Medicinal Product
DMP	Data Management Plan
DSMC	Data and Safety Monitoring Committee
DVS	Data Verification Site
EQ-5D	EuroQoL-5D
GCP	Good Clinical Practice
GMP	Good Manufacturing Practice
GP	General Practitioner
HDPE	High-density polyethylene
HRQL	Health-related quality of life
HUI	Health Utility Index
IB	Investigators Brochure
ICU	Intensive Care Unit
IMP	Investigational Medicinal Product
LRTI	Lower Respiratory Tract Infection
MHRA	Medicines and Healthcare products Regulatory Agency
MIC	Minimum inhibitory concentration ( i.e. the lowest concentration of antimicrobial that will inhibit the visible growth of a micro-organism after overnight incubation)
mls	Millilitres, volume of antibiotic or placebo to be taken by the child
ISF	Investigator Site File
NRES	National Research Ethics Service
PC-CTU	Primary Care – Clinical Trials Unit
PE	Pulmonary Embolism
PI	Principal Investigator

PSC	Programme Steering Committee
PSS	Personal Social Service
QALY	Quality-Adjusted Life-Years
QoL	Quality of Life
QP	Qualified Person
R&D	NHS Trust R&D Department
RCT	Randomised Controlled Trial
REC	Research Ethics Committee
SAE	Serious Adverse Event
SAR	Serious Adverse Reaction
SMPC	Summary of Medicinal Product Characteristics
SOP	Standard Operating Procedure
SUSAR	Suspected Unexpected Serious Adverse Reactions
TSC	Trial Steering Committee
VAS	Visual Analogue Scale

## 1. OVERVIEW OF RESEARCH

### 1.1. DESIGN

RCT nested in an observational study.

### 1.2. SETTING

Primary care defined as first point of contact, this maybe a General Practice or a Hospital Children's Emergency Department.

### 1.3. PRIOR LITERATURE

Cochrane/Medline searches identified no placebo-controlled trials of antibiotics for children with uncomplicated Lower Respiratory Tract Infection (LRTI).

### 1.4. TARGET POPULATION

Children 6 months to 12 years.

### 1.5. INCLUSION CRITERIA

Acute uncomplicated LRTI (acute cough as the most prominent symptom and lower tract symptoms/signs (sputum/'rattly chest'/coarse rhonchi; breathless; pain), Parent/guardian willing and able to be contacted for follow up and complete symptom diary for up to 28 days.

### 1.6. EXCLUSION

Non-infective (e.g. reflux, Pulmonary Embolism (PE)) or croup (where viral aetiology is very likely). Those with clinically suspected pneumonia or very unwell and/or unwilling to be randomised will be invited to participate in an observational study collecting the same data.

### 1.7. Baseline measures

Structured history/examination; pulse oximetry; optional x-ray (for clinically undetected consolidation); and optional samples: swabs (for microbiology) and pinprick blood sample (for CRP and Full blood count). The x-ray will take place in a facility with suitably trained staff and safety measures local to the recruiting site with the site being responsible for the optional samples.

## 1.8. Measurement of costs/outcomes

Primary outcome: duration of moderately bad symptoms (from validated symptom diary). Secondary outcomes: symptom severity (days 2-4); duration of symptoms until very little problem; the development of new or worsening symptoms; complications. Health related quality of life will be measured by proxy methods in which The EuroQoL (EQ5DY) will be completed by patients or carers for age older than 7, children will complete the questionnaire separately too on days 0,1,3, 7, 14 21 and 28. Follow-up (at 1 month): measure lung function (if aged 6+).

Outcome parameters for observational study: development of new or worsening symptoms; complications, diagnosis of pneumonia based on chest X-ray.

## 1.9. Sample size

938 children are required (for alpha=0.01, 90% power, 80% follow-up) to detect a 3 day difference in the effect of antibiotics for the primary outcome among any one of 5 clinical subgroups (see below). We assume a subgroup represents at least 30% of the sample (our data suggests 30-65% for each of the key subgroups).

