Although trials among adults suggest modest benefit even among important clinical subgroups, (10-12) we are aware of no randomised placebo-controlled trials available to either support or dispute the common use of antibiotics in children with chest infections. A national research priority is to do clinical trials of medicines in children to ensure children are better represented in RCTs and that medicines for children are more evidence based. Because of the lack of evidence in children it is difficult for doctors to go against the rising tide of antibiotic use to reduce prescribing antibiotics for children. It may be that antibiotics in children also have limited benefit, however the differences in immunity and anatomy between adults and children prohibit simply applying evidence derived in adults to the management of children. (13) If reduction in antibiotic prescribing is to be achieved, one of the key issue for patients and clinicians is the difficulty of knowing whether the child presenting is an 'average' child: as with adults there is likely to be variation in pathophysiology and disease severity among children with acute cough. (10, 14-16) It is highly unlikely that antibiotics are never indicated in a child with acute cough but there is very limited evidence to support doctors in targeting antibiotics. Therefore it is not surprising that important prescribing decisions are made by doctors using traditional but non-evidence based clinical signs like sputum production, fever, chest signs and being

unwell as indications for antibiotic use. (17-21) The latter data in adults is supported by data in 430 children in our ongoing observational study of acute infective cough – the key driver for antibiotic prescription for examination is the presence of crepitations (present in 40% of children). Symptomatic predictors of prescribing include productive cough ('wet cough/rattly chest/sputum'), shortness of breath, audible wheeze and fever, which are present in between 30% and 65% of children presenting with chest infections, and this has not changed over the last 10 years since our previous trial which included 100 children. (9)

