## 5.15. Sample size calculation

Pilot phase: there is no sample size calculation.

Main phase: An alpha of 0.01 is chosen to allow for 5 pre-specified subgroups, which occur in at least 30% of children based on our previous data (sputum (65%), fever (64%); generally unwell rated as a bad problem (30%); short of breath (36%) abnormal chest signs (crepitations: 43% ). Previous consensus documented less than 2-3 days difference in symptoms rated moderately bad or worse is unlikely to be a sufficient reason to prescribe antibiotics, and 3 days should probably now be the minimum given the short and long term disadvantages of antibiotics, (9, 10) and in particular increased national and international concern over the danger of antibiotic resistance (<https://www.gov.uk/government/publications/resources-to-support-the-2012-european-antibiotic-awareness-day-in-england>; <https://www.gov.uk/government/news/prime-minister-warns-of-global-threat-of-antibiotic-resistance> ). (3, 4) To detect a hazard ratio for the treatment interaction of 1.7 (see Appendix 2 to this protocol: equivalent to 3 days difference between a subgroup and the whole sample), for the smallest subgroup of interest (30% of the sample), using the equations of Schmoor et al requires 738 individuals for 80% power and 938 individuals for 90% power (assuming 80% follow-up). (36) The other (larger subgroups) will have greater power. To allow for some leeway in our assumptions we will aim to recruit at least 1000 children.

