### 9.3. The Level of Statistical Significance

A 5% significance level will be used for testing effects in the whole cohort and a 1% significance level for the testing of subgroup interactions, as per the sample size calculation.

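### The subgroup power statement has a floor (30%) but no ceiling: interaction power is symmetric about a 50% share, so a subgroup above 70% has less power than the 30% subgroup that set the sample size

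*Protocol*

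**What the plan says.** Section 1.9 asks for 938 children (alpha 0.01, 90% power, 80% follow-up) and gives the condition on subgroup size: "We assume a subgroup represents at least 30% of the sample (our data suggests 30-65% for each of the key subgroups").

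Section 5.15 sizes the trial "To detect a hazard ratio for the treatment interaction of 1.7", "for the smallest subgroup of interest (30% of the sample"), and "requires 738 individuals for 80% power and 938 individuals for 90% power (assuming 80% follow-up"). It lists the expected shares as sputum 65%, fever 64%, generally unwell 30%, short of breath 36% and chest signs 43%. It then says "The other (larger subgroups) will have greater power" and raises the recruitment aim to at least 1000 to give some leeway. Section 9.3 confirms the test: "a 1% significance level for the testing of subgroup interactions, as per the sample size calculation".

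Three other places bear on the point:

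- Section 1.10 calls the five subgroups provisional, to be finalised in the analysis plan blind to allocation. Its sputum subgroup counts sputum noticed by parents (rattly chest) or found by the clinician on examination.
- Section 1.5 makes entry depend on "lower tract symptoms/signs (sputum/'rattly chest'/coarse rhonchi; breathless; pain"). Section 5.4 names sputum alone as the lower-tract feature.
- Section 3 takes the planning shares from "data in 430 children in our ongoing observational study of acute infective cough", and describes these features as present in 30% to 65% of children presenting with chest infections.

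**The concern.** A lower bound alone would be enough if power rose steadily with subgroup size. That is how the power of a treatment comparison made inside the subgroup behaves. An interaction compares the treatment effect inside the subgroup with the effect outside it, so a very large subgroup leaves too few children on the other side. The worst case is then the share furthest from 50% in either direction, not simply the smallest subgroup.

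Section 3 argues that a trial powered only for the average effect would not persuade prescribers, so the subgroup tests carry much of the design. If one subgroup turned out at 80% or 90% of the sample, the protocol's wording would credit it with more power than the 30% subgroup when it has less. A null interaction there could be given more weight than it deserves.

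**Working it through.** **Inputs.** Interaction hazard ratio 1.7, N = 938 for 90% power and 738 for 80%, 80% follow-up, and the five shares (section 5.15); alpha 0.01 (sections 1.9 and 9.3). Assumptions: a two-sided test, 1:1 allocation, and every followed-up child contributing an event. Two-sidedness fits the protocol's own ratio: 938/738 = 1.271, against (2.576 + 1.282)² / (2.576 + 0.842)² = 14.879/11.679 = 1.274.

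**Step 1: the protocol's figure.** The direct formula for an interaction of two binary factors in a Cox model is

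events = (z_{α/2} + z_{power})² / [0.25 × q(1−q) × (ln HR)²].

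At q = 0.30: 14.879 / (0.25 × 0.21 × 0.2816) = 1,007 events. Dividing by 0.8 gives 1,259 children for 90% power; the same steps give 988 for 80%. The stated 938 and 738 are **not reproduced**. By this formula, 938 children give 77.5% at q = 0.30.

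**Step 2: the shape.** The subgroup share enters only through q(1−q). Since 0.30 × 0.70 = 0.70 × 0.30 = 0.21, shares of 30% and 70% have equal power whatever the correct N.

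**Step 3: the size.** Accepting the protocol's 90% at 30% with 938 children:

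power = Φ(3.857 × √[(N/938) × q(1−q)/0.21] − 2.576).

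The last column uses the direct formula without that calibration.

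| Share q | q(1−q) | Calibrated, N = 938 | Calibrated, N = 1000 | Direct, N = 938 |
|---|---|---|---|---|
| 30% (unwell) | 0.2100 | 90.0% | 92.0% | 77.5% |
| 36% (short of breath) | 0.2304 | 92.8% | 94.5% | 81.9% |
| 43% (chest signs) | 0.2451 | 94.4% | 95.8% | 84.7% |
| 50% | 0.2500 | 94.9% | 96.2% | 85.5% |
| 64% (fever) | 0.2304 | 92.8% | 94.5% | 81.9% |
| 65% (sputum) | 0.2275 | 92.5% | 94.2% | 81.3% |
| 70% | 0.2100 | 90.0% | 92.0% | 77.5% |
| 71% | 0.2059 | 89.3% | 91.4% | 76.5% |
| 75% | 0.1875 | 85.7% | 88.3% | 71.6% |
| 80% | 0.1600 | 78.6% | 81.6% | 63.0% |
| 90% | 0.0900 | 48.0% | 51.3% | 34.6% |

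With 1000 children the calibrated 90% holds while q(1−q) ≥ 0.21 × 938/1000 = 0.197, that is up to q = 0.5 + √(0.25 − 0.197) = 73%.

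A Cox simulation with 750 events and 1,000 runs per share shows the same shape and agrees with the direct column: 77.0% at a share of 30%, 86.8% at 50%, 80.3% at 65%, 78.5% at 70%, 60.3% at 80% and 35.5% at 90%.

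**Step 4: could sputum pass 70%?** The protocol gives no sputum share under its own entry rule, so this step is illustrative only. Assume that the planning shares describe children before the entry rule is applied, that the features are independent, and that pain (no figure given) lies between 0 and 30%. A child without sputum can enter under section 1.5 through breathlessness (36%), chest signs (43%) or pain:

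share = 0.65 / [1 − 0.35 × 0.64 × 0.57 × (1 − pain)].

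This gives 0.65/0.872 = 75% with no pain and 0.65/0.911 = 71% with pain at 30%. Calibrated power is then 86% to 89% with 938 children and 89% to 91% with 1000. Under section 5.4 read literally, with sputum the only qualifying feature, the share would approach 100% and the comparison group would almost vanish.

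**The case against.** The strongest reply is that the sentence on larger subgroups refers to the four shares listed just before it (36%, 43%, 64% and 65%), and for these it is true. Section 1.9 also gives the upper planning value of 65% in the same sentence as the floor. This stands: on the protocol's planning shares there is no false power claim. What remains is a rule without a ceiling, applied to subgroups that section 1.10 calls provisional.

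A reader might infer that the sputum share among randomised children must exceed 65%, because the planning data come from a cough cohort and the trial selects on lower-tract features. The documents do not support that. Section 3 describes the source children as presenting with chest infections and says the pattern has not changed since a previous trial that included 100 children. Section 5.12 describes a trial of 100 children as using the same entry criteria as this one. The cohort may therefore already reflect much of the entry selection. A reader might also put the share at 77% to 84% by allowing entry without sputum only through breathlessness or pain. That leaves out coarse rhonchi, which section 1.5 lists as an entry feature and section 1.10 places in the separate chest-signs subgroup; including it gives the 71% to 75% above.

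A further reply is that the larger recruitment aim covers the problem. It does, on the protocol's calibration, up to a 73% share and no further.

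Finally, 938 is close to what a treatment comparison inside the 30% subgroup would need: by Freedman's formula, 14.879 × (2.7/0.7)² gives 222 events, and 222/0.3/0.8 = 925. For such a comparison, power would indeed rise with share. A reader might infer that this is how 938 was obtained. The match is not exact, and sections 5.15 and 9.3 both specify an interaction test, so the documents do not establish it.

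**Conclusion.** The point holds as a correction of wording with a conditional consequence. A floor of 30% does not secure the stated power for an interaction test, and larger subgroups have greater power than the 30% subgroup only up to a 70% share. The symmetry is exact under the variance formula and does not depend on whether 938 is right.

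No planning share breaches the limit. Sputum comes closest and is the only one of the five that section 5.4 makes an entry feature on its own. Whether it passes 70% cannot be settled from the protocol. If it did, the loss would be slight at 71% to 75% (89% to 86% with 938 children) and large at 80% to 90% (79% to 48%).

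These figures accept the protocol's 90% at 30%. By the direct formula 938 children give 77.5% at 30% or 70% and at most 85.5% at any share. It would therefore be wrong to conclude that 90% is assured between 30% and 70%.

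**What to change.** 1. In sections 1.9 and 5.15, replace the condition of at least 30% with a range of 30% to 70%.
2. Limit the sentence on larger subgroups to that range, and say that such subgroups have at least the power of the 30% subgroup. Do not word it as a guaranteed 90%.
3. Reconcile the lower-tract features in sections 1.5 and 5.4, and state the sputum share expected under the reconciled wording.
4. When the subgroups are finalised blind, tabulate the pooled baseline share of each and state the power for any outside 30% to 70%.
5. Before restating any power, recheck 938 and 738 against the interaction formula and record the method and assumptions used.

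Items 1 to 4 need wording and a table of baseline counts already collected, with no unblinding and no extra children. Item 5 needs a short recalculation, and the stated power may turn out less favourable.

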## 1.10. Subgroups

Our provisional approach is to the following subgroups but this will be finalized in the analysis plan, the decision being made blind to the intervention group.

- Sputum seen and/or heard by parents ('rattly chest') or by clinician on clinical examination
- History of fever
- Physician rating of being unwell
- Short of breath
- Chest signs (non-focal coarse crepitations/rhonchi/wheeze).

## 1.11. Analysis

Data will be available as anonymized to the study analysts. All study staff must comply with the requirements of the Data Protection Act 1998 with regard to the collection, storage, processing and disclosure of personal information.

Computers used to collate the data will have limited access measures via usernames and passwords. Information will be kept on an encrypted drive and backed up on a daily basis. Should the password-protected computer be stolen or mislaid, data from the study will remain available via backups made and access to this data protected from external parties by placing the data on an encrypted drive.

Should secure access to data from the questionnaire software be compromised, a member of the study team will download available data from the website and immediately remove the survey and data.

Disseminated results will not contain any personal identifiable data of individual participants.

Cox proportional hazards models will provide estimates both overall and for subgroups and estimates of interaction with intervention by subgroup. In addition we will explore to what extent results from additional tests (bacteriology, biomarkers, abnormalities on chest-X rays, etc) are potential effect modifiers, and will explore differences between the purely observational data set and the trial data and other large observational cohorts.(1, 2) We will conduct economic evaluation alongside the clinical trial. Costs will take an NHS and personal social service (PSS) perspective (primary analysis) and societal perspective (secondary analysis). If the intervention is proved to be effective, we will estimate as the costs per symptomatic day prevented and the incremental costs per QALY gained. Cost effectiveness acceptability curves will also be produced to illustrate the uncertainty. Also we aim to develop a diagnostic model to detect pneumonia and assess to what extent additional tests have added diagnostic value. In addition we also analyse the prognostic value of patient characteristics to assess disease severity and identify high risk patients.

## 2. LAY SUMMARY

Although chest infections are one of the commonest infections managed in children seen in primary care, there have been no placebo controlled trials to show what effect antibiotics have - in contrast to adults where there is now good trial evidence to show that for most people antibiotics do not work. The trouble with prescribing for most children is that antibiotics are being used too much which is causing the bacteria to become resistant, which is likely to lead in the future to serious infections for our children becoming untreatable from 'superbugs'. Most children who see the doctor with a chest infection currently get antibiotics, and the groups of children that are even more likely to get antibiotic treatment at the moment are those who have one or more particular features - phlegm, fever, shortness of breath, or rattly noises heard in the chest when the doctor listens with the stethoscope. It is a real priority to show which groups of children that doctors prescribe for currently benefit and which do not, so that antibiotics can be targeted appropriately and the effectiveness of antibiotics can be conserved for future generations.

In the study more than 900 children with chest infections presenting in primary care will be allocated by random numbers to either get amoxicillin (an antibiotic) or not get amoxicillin for 1 week, and see whether antibiotics make any difference to symptom severity, or the duration of illness. All children will be given advice about using painkillers and will be followed up carefully during the next month. The study will be large enough to be able to show which, if any, groups of children that doctors currently prescribe for benefit from antibiotics (such as those with fever compared to those with no fever), and which groups do not. Parents and children who are happy to have further tests will have any, or all, of a pinprick blood sample taken, a swab of the throat taken and an X-ray done. This is to

see whether simple markers of inflammation and infection or the presence of bacteria, or any lung involvement seen on the X-ray can predict benefit from antibiotics.

### 3. BACKGROUND AND RATIONALE

Acute respiratory infections are among the commonest conditions managed in primary care. The Department of Health recognises that antibiotic resistance is an increasingly serious public health problem in England, Europe and the world with rising resistance rates for a range of antibiotics, and a clear relationship between primary care antibiotic prescribing (responsible for 80% of prescribing) and antibiotic resistance. (3, 4) The costs of resistance are also often not included in current estimates of cost-effectiveness. (4) Although consultations rates and antibiotic prescription rates for URTI or chest infections declined sharply in the late 1990s until the early 2000s (consultation rate 160/1000 for females; 120/1000 for males), (5) it is clear that antibiotic use is rising again and the volume of antibiotics prescribed has now exceeded the peak in the late 1990s (<https://www.gov.uk/government/publications/resources-to-support-the-2012-european-antibiotic-awareness-day-in-england>). (4) The Chief Medical Officer of England has recently warned of catastrophic dangers posed by the overuse of antibiotics, with a key proposed solution of the increased quality of decisions about prescribing our existing antibiotics.

Children have higher consultation rates for respiratory tract infections than adults, and even when antibiotic prescription was at its lowest most children labelled as having URTI or chest infection still were prescribed antibiotics. (6) Data from our current ongoing observational study among children confirms that at least 60% of children are prescribed antibiotics, which translates to 3 million prescriptions for antibiotics for cough in this age group (6, 7) or approximately 41 million pounds annually in direct consultation and dispensing costs, let alone the indirect costs incurred by 'medicalising' illness in the family and wider social networks. (8, 9)

Although trials among adults suggest modest benefit even among important clinical subgroups, (10-12) we are aware of no randomised placebo-controlled trials available to either support or dispute the common use of antibiotics in children with chest infections. A national research priority is to do clinical trials of medicines in children to ensure children are better represented in RCTs and that medicines for children are more evidence based. Because of the lack of evidence in children it is difficult for doctors to go against the rising tide of antibiotic use to reduce prescribing antibiotics for children. It may be that antibiotics in children also have limited benefit, however the differences in immunity and anatomy between adults and children prohibit simply applying evidence derived in adults to the management of children. (13) If reduction in antibiotic prescribing is to be achieved, one of the key issue for patients and clinicians is the difficulty of knowing whether the child presenting is an 'average' child: as with adults there is likely to be variation in pathophysiology and disease severity among children with acute cough. (10, 14-16) It is highly unlikely that antibiotics are never indicated in a child with acute cough but there is very limited evidence to support doctors in targeting antibiotics. Therefore it is not surprising that important prescribing decisions are made by doctors using traditional but non-evidence based clinical signs like sputum production, fever, chest signs and being

unwell as indications for antibiotic use. (17-21) The latter data in adults is supported by data in 430 children in our ongoing observational study of acute infective cough – the key driver for antibiotic prescription for examination is the presence of crepitations (present in 40% of children). Symptomatic predictors of prescribing include productive cough ('wet cough/rattly chest/sputum'), shortness of breath, audible wheeze and fever, which are present in between 30% and 65% of children presenting with chest infections, and this has not changed over the last 10 years since our previous trial which included 100 children. (9)

